22 The **rate of rehospitalization or emergency room visits** will be evaluated during the  
23 telephone call made by a research assistant at D30 post hospital discharge. The cause of  
24 hospitalization will be determined by means of the computerized hospital patient file if he is  
25 rehospitalized at the HUG or *saycté* to the patient (or his attending physician depending on the  
26 patient's cognitive functions) if he is hospitalized in another hospital. It is interesting to assess  
27 whether the patient consumed unplanned care and whether it was related to instability of his  
28 heart failure. This outcome was not chosen as a primary indicator because of the need to  
29 include very large cohorts (>1000 participants) to demonstrate a statistically significant impact  
30 as shown in the scientific literature in this area to date (5,11,30,39,67,68).  
31

32 The **rate of death at 1 month after hospitalization** will be assessed in both groups. This  
33 information can be collected from the participants' computerized patient records if mentioned  
34 or from the participants' relatives or attending physician.  
35

36  
37 The **use and usability of the mobile smartphone application** (CardioMeds®) will be explored  
38 by the research assistant during the telephone call at D30 post hospital discharge using a  
39 validated standardized questionnaire (69) (Appendix 9). This tool to help with medication  
40 administration was developed specifically for patients with heart failure and jointly by the  
41 Cardiology Department, the Information Systems Department and the Pharmacy Department  
42 of the HUG. It includes some of the information provided during the teaching and offers the  
43 participant the possibility to create and use his electronic medication plan and to follow some  
44 parameters of self-administered care such as weight and symptoms monitoring. It will be  
45 offered to study participants by the pharmacist investigator during the pre-discharge interview.  
46 If the patient wishes to use it for their return home, the investigating pharmacist will install the  
47 application on the participant's smartphone/tablet and explain how to use it.  
48

49 The **self-care skills** of patients using CardioMeds® will be explored using a validated  
50 questionnaire composed of 22 questions (70) (Appendix 10) to measure the effect of this  

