51 application on patients' level of empowerment in their care.  
52  
53

[figure not shown]
1 During hospitalization, the four questionnaires (knowledge, beliefs, therapeutic adherence,  
2 and satisfaction) will be sent to the participants in paper or electronic format (on a tablet)  
3 according to the patient's wishes by the pharmacist investigator or the research assistant.  
4 These questionnaires will be sent again to the participants at 1 month after discharge from  
5 hospital, as well as the two questionnaires for the participants using CardioMeds®. They will  
6 be sent either by e-mail or by post to be completed by the patient and returned to the  
7 investigator. In the event that these questionnaires are not returned, they will be addressed  
8 orally during a telephone interview by a research assistant.

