The pharmacist will ensure that the following elements of continuity of care are established:

- the patient has a community pharmacy where he/she can collect his/her medication and which can follow him/her;
- the organization of the medication at home is adapted to the needs and lifestyle of the patient;
- Resource persons are identified when needed.

He will give the patient a document in the form of a "memory card" that will highlight the important key points of the heart failure medication education. It is the patient himself, during this interview, who will take care to complete this document to visualize his current list of heart failure medications and the adverse effects to be followed. A flyer entitled "control of heart failure" developed by the Cardiology Service of the HUG will be given to them so that they have a reference scale to rely on to evaluate their symptomatology and the need to consult or not and to remember the good self-care gestures to adopt at home. At this stage, the patient will also be asked if he/she would like to have a treatment card in paper format (made by the internal physician) or in digital format available on a smartphone (CardioMeds®).

In case the patient wishes to benefit from this digital tool, the CardioMeds application® will be presented and installed by the pharmacist.

3. The **third step of the intervention** consists of a telephone call to the patient between D3 and D7 after discharge from hospital by the pharmacist (including patients who have stayed in a rehabilitation unit). This call will allow the pharmacist to ensure that the patient has picked up their medications and is clear on their treatment plan. It will also serve to ensure that the patient is not showing signs of decompensation of their heart failure. He or she will be available for any questions the patient may have regarding his or her health and will refer the patient to the appropriate resource people if necessary.

The tools used to create the teaching interview and the pedagogical scenario were developed by a clinical pharmacist in general internal medicine, inspired by existing tools for heart failure patients and helped by the information needs of heart failure patients at the HUG, the opinion of two patient partners, and the opinion of health professionals at the HUG (clinical pharmacists, cardiologist, nurse).

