#### Assessment of the level of knowledge (primary outcome):

The level of knowledge of the patients will be assessed in the intervention group by a questionnaire (Appendix 1) on three occasions: at time 0 before any intervention as a pre-test, after the teaching interview as post-test n°1 and finally at 1 month post-discharge as post-test n°2.

This questionnaire will be proposed in the control group at time 0 (pre-test) and at 1 month after hospitalization (post-test).

During hospitalization, the questionnaire will be sent to the patient by the investigating pharmacist and will be completed by the patient himself with the help of the pharmacist if necessary.

At 1 month after discharge, the questionnaire will be sent to the patient by email or post. If no return is obtained, the research assistant will address the questionnaires to them during a phone call.

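### The 1-month knowledge test is taken unsupervised at home, and the intervention arm holds trial handouts covering part of it, so look-up during the test may differ by arm and is neither discouraged nor recorded

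*Combined protocol and SAP*

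**What the plan says.** The primary analysis (Section 5.1) compares 1-month knowledge scores between arms, adjusted for the baseline score. Section 3.1 also asks whether the level reached after the interview is still present 30 days after discharge.

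**How the test is taken.** In hospital the questionnaire "will be completed by the patient himself with the help of the pharmacist if necessary". For the 1-month test, Section 4.3 says: "At 1 month after discharge, the questionnaire will be sent to the patient by email or post". Section 3.2 says the forms will "be sent either by e-mail or by post to be completed by the patient and returned to the" investigator. The fallback is: "If no return is obtained, the research assistant will address the questionnaires to them during a phone call". Table 2, however, gives a patient interview as the source of the 1-month knowledge questionnaire (item 79).

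**What intervention patients hold by then.** At the pre-discharge interview (Section 3.4, part 2) the pharmacist hands over a memory card "that will highlight the important key points of the heart failure medication education", on which the patient writes his or her heart failure drugs and the adverse effects to watch for. A Cardiology Service flyer on symptoms, self-care and when to seek care is given too, and the app is offered. Of the app, Section 3.2 says "It includes some of the information provided during the teaching and offers the" participant a medication plan and symptom tracking. Controls receive usual care without this interview.

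**What the test asks.** According to Section 3.2, 11 of the 17 questions concern medications, including which drugs treat heart failure, what they are for, and their adverse effects. Six concern the disease, including symptoms of decompensation and how to respond.

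**The concern.** The score is meant to show what patients know. Completed alone at home, it can also show what they looked up. Trial materials covering part of the content are given in the intervention arm, so the opportunity is not clearly equal between arms.

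The materials arrive after baseline, so neither randomization nor adjustment for the pre-test score removes a difference that arises from using them during the test. They also arrive after the immediate post-test, so the within-arm comparison of that test with the 1-month test is exposed as well.

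The main text contains no instruction to answer without aids, no data item for use of aids or for the actual completion mode, and no analysis by either. If look-up occurred, the trial could not detect it or estimate its effect. At stake is an overstated primary difference.

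**Working it through.** **1. The plan's own figures.** 30% of 7.95 is 2.385, the stated 2.39 points. The stated 40 per group does not follow from SD 2.67 (two-sided 5%, 80% power, t-test: 20.6, so 21 per group). It does follow from SD 2.67 × √2 = 3.776 (40.2), an SD the documents do not state. Both SDs are therefore used below.

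**2. Overlap, set side by side (Sections 3.2 and 3.4).**

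| Material | Holder | Tested topics it touches |
|---|---|---|
| Memory card | Intervention patients who have the pre-discharge interview | Identifying heart failure drugs; adverse effects |
| Flyer | Intervention arm; control access not stated | Symptoms; when and how to act |
| App | Intervention patients who accept it | Some of the teaching content |

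The overlap is partial. Nothing in the description of the card or flyer shows that they cover the definition of the disease, precipitating factors, treatment duration or missed doses.

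**3. Size, under assumptions.** The documents give no look-up rate or gain. Assume 20% to 30% of intervention patients look up answers and gain 2 to 4 points each, that no controls do, and that there is no true effect.

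- Shift = share × gain: 0.20 × 2 = 0.4 points; 0.30 × 4 = 1.2 points.
- Relative to the target: 0.4/2.39 = 17%; 1.2/2.39 = 50%.
- Standard error at 45 per group: 2.67 × √(2/45) = 0.563.
- Noncentrality: 0.4/0.563 = 0.71; 1.2/0.563 = 2.13.
- Probability that a two-sided 5% t-test (88 df, critical value 1.987) is significant:

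| Setting | Shift 0.4 | Shift 1.2 |
|---|---|---|
| 45 per group, SD 2.67 | 10.8% | 55.9% |
| 62 per group (expected enrolment), SD 2.67 | 13.1% | 69.9% |
| 45 per group, SD 3.776 | 7.9% | 32.0% |

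**4. Effect of the missing-data rule.** Sections 5.1 and 5.2 put the baseline value in place of a missing post-test. With the anticipated 10% loss, the shifts shrink to 0.9 × 0.4 = 0.36 and 0.9 × 1.2 = 1.08. Holding SD at 2.67 and 45 per group, the probabilities are 9.7% and 47.5%.

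**5. Effect of baseline adjustment.** The planned ANCOVA moves the figures the other way. For a shift of 1.0 point at 45 per group (normal approximation), the probability is 43% unadjusted and 54% with an assumed pre-post correlation of 0.5 (residual SD 2.67 × √0.75 = 2.31).

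**The case against.** - **The handouts belong to the intervention.** This stands. The research question is whether the educational package improves knowledge, and reading the card at home beforehand is part of how it may work. A reader might infer that the trial cannot answer its own question. The documents do not support that: only consultation during the test is at issue.
- **Controls can look things up too.** This stands in part. The flyer comes from the Cardiology Service, and nothing says usual-care patients never receive it. In usual care the physician hands out a prescription and a treatment plan (Section 3.4), and Table 2 asks about internet at home. A reader might infer that any look-up favours the intervention arm. The text supports only that it may, and only the net difference between arms matters. The memory card, however, comes only through the pharmacist's interview.
- **The size is invented.** It is assumed throughout. Eight multiple-choice questions give half a point for a partly correct answer, so gains per question may be smaller than a full point. The SD comes from 10 patients.
- **The form may already carry an instruction.** Appendix 1 is not in the text available here, so this cannot be excluded. Use of aids would still be absent from Table 2 and the analyses.
- **Mode is partly known.** Table 2 records contact preference, and e-mailed forms go out through REDCap. Preference is not the mode actually used.
- **Test everyone by telephone.** This is tempting because a "telephone call made by a research assistant at D30 post hospital discharge" is already planned. It is a trade-off, not a clear gain. The same assistant asks app questions that apply only to intervention patients, so is probably not blind, and would stand between patient and score, including three open questions marked subjectively. Everyone would move from a written pre-test to an oral post-test, and a patient can still hold the card during a call.

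**Conclusion.** The concern holds in a limited form. The 1-month primary test is unsupervised, the intervention arm holds trial materials that overlap part of it, and nothing in the main text discourages or records their use while answering. Look-up may therefore differ by arm and inflate apparent retained knowledge.

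The size cannot be derived from the documents. The 11% to 56% range is an illustration that assumes no true effect, no look-up by controls, 45 per group and SD 2.67. Other inputs move it in either direction, as shown above. It does not show that a positive result would be spurious. It shows that a modest net look-up could matter against a 2.39-point target, which justifies a cheap safeguard and a measurement. Handing out the materials and posting the form both remain acceptable.

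**What to change.** In Section 3.2 (the closing text on sending the questionnaires), Section 4.3 (assessment of the level of knowledge) and Table 2:

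1. Unless Appendix 1 already does so, state on the 1-month form and in the telephone fallback script, in identical words for both arms, that the knowledge questions are to be answered without documents, app, internet or help from another person.
2. Add one yes/no item in both arms asking whether any such aid was used.
3. Record the actual completion mode: paper, e-mail or telephone.
4. In Section 5.1, pre-specify a sensitivity analysis of the primary comparison by reported aid use and by mode. Label it supportive, because both are post-randomization variables and excluding or adjusting on them no longer gives a purely randomized comparison.
5. Reconcile the interview source given in Table 2 for the 1-month knowledge questionnaire with the posted or e-mailed form in Sections 3.2 and 4.3.

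The cost is one extra item, one data field and one extra analysis. Self-reported aid use may be under-reported, so the sensitivity analysis can reveal a problem but cannot rule one out.

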#### Assessment of beliefs about medications (secondary outcome)

Beliefs about medicines will be assessed indirectly using the Beliefs about Medicines Questionnaire (Appendix 3) at time 0 (pre-test) after obtaining the consent form and at 1 month after hospitalization (post-test) in both groups.

During hospitalization, the questionnaire will be sent to the patient by the investigating pharmacist and it will be filled in by the patient himself with the help of the pharmacist if necessary. One month after discharge, the questionnaire will be sent to the patient by email or post. If no return is obtained, the research assistant will send them the questionnaires during a telephone call.

#### Assessment of therapeutic adherence (secondary outcome)

Adherence to therapy will be assessed for all participants with the 3-item self-report questionnaire (Appendix 4) on two occasions. It will be presented to the participant by the investigator at time 0 after obtaining the consent form (pre-test), as well as at 1 month post-hospitalization. During hospitalization, the questionnaire will be sent to the patient by the investigating pharmacist and completed by the patient himself with the help of the pharmacist if necessary.

At 1 month after discharge, the questionnaire will be sent to the patient by email or post. If no return is obtained, the research assistant will address the questionnaires to them during a phone call.

#### Rate of rehospitalization and emergency room visits (secondary outcome)

All study participants will be asked during the 1-month postdischarge telephone call whether they have been readmitted to the hospital since discharge and for what reason, whether they have been seen in the hospital or by their physician for signs of cardiac decompensation.

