75	Heart failure medication list	Patient interview	Date: (...../...../.....)  Specialty / INN / Dosage / Dosage e.g. Forxiga, dapagliflozin, 10mg, i.d
76	Adverse drug reactions	Patient interview	 Extreme fatigue  Dizziness when you stand up  Vision problems  Headaches  A frequent need to urinate  Low blood pressure (<110mmHg)  A low heart rate (<60 bpm)  Rapid weight gain (>2kg in 3 days)

			 Worsening of shortness of breath or edema  Dry cough  Dry mouth and intense thirst  Dry skin
77	Physical and moral feelings of the patient on returning home	Patient interview	Free response
78	Experience and feeling of going home	Patient interview	Free response
Post-test data at 1 month			
79	Knowledge Questionnaire	Patient interview	Answer for each question (detailed in the documents specific to the questionnaires)
80	Score	Calculation	Value:
81	Belief questionnaires	Patient interview	Answer for each question (detailed in the documents specific to the questionnaires)
82	Score need	Calculation	Value:
83	Concern score	Calculation	Value:
84	Differential score	Calculation	Value:
85	Membership questionnaire	Patient interview	Answer for each question (detailed in the documents specific to the questionnaires)
86	Score	Calculation	Value:
87	Satisfaction questionnaire	Patient interview	Answer for each question (detailed in the documents specific to the questionnaires)
88	CardioMeds Usability Questionnaire	Patient interview	Answer for each question (detailed in the documents specific to the questionnaires)
89	CardioMeds Self-Care Questionnaire	Patient interview	Answer for each question (detailed in the documents specific to the questionnaires)
90	Heart failure medication list	Patient interview	Date: (...../...../.....)  Specialty / INN / Dosage / Dosage e.g. Forxiga, dapagliflozin, 10mg, i.d
91	Re-hospitalization 1 month after hospitalization	Patient interview	 Yes  No
92	Emergency visits (Hospital/Ambulatory ) 1 month after hospitalization	Patient interview	 Yes  No

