93	Deaths 1 month after hospitalization	Medical records, relatives, attending physician	 Yes  No

\*This participant identification data will not appear in the participant's Case Report Form (CRF). It will be collected by the investigator and stored separately from the CRF in a secure electronic file accessible only by the investigator and the CRA.

\*\* The e-mail address will be visible in the eCRF but only consultable by the investigator and the clinical research associate. It must appear in the CDMS (RedCap™) to allow the setting of the sending of the questionnaires at 1 month for the participants having wished to receive them by e-mail. As soon as all the participant's data have been collected and the study is closed, the e-mail addresses will be deleted from the CDMS.

For any data that is not complete during hospitalization, it will be obtained by phone call upon the participant's return home.

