#### Death rate (secondary outcome)

In case of non-response of participants to the post-test questionnaires, it will be investigated by means of the computerized patient record of the hospital or with the relatives or the attending physicians in charge of the participants if the participants died within one month of the hospital discharge.

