#### **4.4 Withdrawal and interruption**

A participant may withdraw from the study at any time if he or she no longer wishes to participate. A participant will be withdrawn from the study if he/she dies, if his/her health condition deteriorates to the point where he/she can no longer meet the inclusion criteria or be physically able to follow the pharmacist's intervention, if he/she loses his/her capacity of discernment, if he/she cannot be reached by telephone after discharge from the hospital.

A study with temporal follow-up is associated with a significant risk of break in follow-up or

withdrawal of informed consent. Therefore, we choose to implement an intention-to-treat analysis. The data collected will be retained until the loss of a participant. The number of lost to follow-up will be specified in the results in the form of a flowchart. All data used in the analysis will be anonymized afterwards.

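### Whether a readmission or emergency visit occurred is asked only of the patient at the 1-month call, so patients who die or are not reached have no result, although the hospital record is already searched for deaths.

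*Combined protocol and SAP*

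**What the plan says.** Section 4.3, under the readmission and emergency-visit outcome, puts the question to the patient: "All study participants will be asked during the 1-month postdischarge telephone call whether they have been readmitted to the hospital since discharge". Section 3.2 agrees that the rate is evaluated at the "telephone call made by a research assistant at D30 post hospital discharge". In Table 2, item 91 ("Re-hospitalization 1 month after hospitalization") and item 92 (emergency visits, hospital or ambulatory) both have the patient interview as their only origin.

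Section 3.2 does mention the hospital file, but for another purpose. The cause of "hospitalization will be determined by means of the computerized hospital patient file if he is" readmitted to HUG; for a stay elsewhere, the patient or the attending physician is asked.

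Death is treated differently. Table 2, item 93, gives its origin as "Medical records, relatives, attending physician", and Section 4.3 adds: "In case of non-response of participants to the post-test questionnaires, it will be investigated by means of the computerized patient record".

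Section 4.4 states: "A participant will be withdrawn from the study if he/she dies". It also withdraws anyone who cannot be reached by telephone after discharge, and it keeps data only up to the loss. The one missing-data rule, in Sections 5.1 and 5.2, carries the baseline knowledge score forward and covers no other outcome. Section 5 nevertheless commits to an intention-to-treat analysis of all randomised patients, and Section 4.2 says that data from patients who die will be considered in the final analysis.

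**The concern.** A patient who is in hospital, very ill or dead at day 30 is poorly placed to take a telephone call. The plan therefore risks losing the outcome in the patients most likely to have had the event. For those patients there is no second source, no imputation rule and no stated place in the denominator. The chi-square or Fisher test would then be run on those who answered and would understate the rate.

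If response differs between the arms, the understatement differs too, and a difference can appear where none exists. The arms do have different contact: only the intervention arm receives the pharmacist's call between D3 and D7 (Sections 3.4 and 4.3).

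**Working it through.** **Sources side by side**

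| Outcome | Did it occur? | Fallback for non-responders |
|---|---|---|
| Readmission (item 91) | Patient interview | None stated |
| Emergency visit (item 92) | Patient interview | None stated |
| Death (item 93) | Records, relatives, attending physician | Record, relatives or physicians (Section 4.3) |

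**Inputs from the protocol.** Loss to follow-up is about 10% and the required size 45 per arm, with 62 per arm expected (Section 5.1). The 30-day readmission rate is 15% as the planning figure, 7% in the hospital's own 2019 data and 25% in the literature (Section 2).

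**Assumptions, not in the protocol.** The risk in those lost is m = 2 or 3 times the average risk. For the between-arm case, non-response is 5% in one arm and 15% in the other.

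**The protocol's own figure.** Section 2 gives about 2544 patients to detect a 3.75-point difference from 15% (15% v 11.25%, alpha 0.05, power 80%). The usual two-sided formula for two proportions, without continuity correction, gives 1272 per arm: 2 × 1272 = 2544. The figure reproduces, and this point does not dispute it.

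**Rate seen among responders.** With true rate r, non-response q and relative risk m in those lost, the observed rate is r(1 − qm)/(1 − q). At r = 0.15 and q = 0.10:
- m = 2: 0.15 × 0.80/0.90 = 13.3%
- m = 3: 0.15 × 0.70/0.90 = 11.7%

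Per 45 patients, 45 × 0.15 = 6.75 events are expected, of which 45 × 0.10 × 0.30 = 1.35 to 45 × 0.10 × 0.45 = 2.03 go unseen.

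**False difference when both arms truly have 15%**
- m = 2: 0.15 × 0.90/0.95 = 14.2% and 0.15 × 0.70/0.85 = 12.4%, a gap of 1.9 points
- m = 3: 0.15 × 0.85/0.95 = 13.4% and 0.15 × 0.55/0.85 = 9.7%, a gap of 3.7 points

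The gap is proportional to r:

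| True rate | m = 2 | m = 3 |
|---|---|---|
| 7% | 0.9 points | 1.7 points |
| 15% | 1.9 points | 3.7 points |
| 25% | 3.1 points | 6.2 points |

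**Bounds without any risk assumption.** With 90 patients and 10% loss, 81 are reached. If 15% of those report an event (12.15), the rate over all 90 lies between 12.15/90 = 13.5% (no event in the 9 lost) and 21.15/90 = 23.5% (an event in all 9).

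**Precision.** With 15% in both arms, the standard error of the difference is √(2 × 0.15 × 0.85/45) = 7.5 points at 45 per arm, a 95% half-width of about 15 points. At 62 per arm the half-width is about 13 points. Power for 15% v 11.25% is about 8% and 9% respectively.

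**The case against.** **The outcome carries little weight.** Sections 2 and 3.2 explain that readmission was deliberately not made primary because the trial is far too small for it. A false difference of 1.9 to 3.7 points is a quarter to a half of one standard error at 45 per arm. This stands, and it limits the severity.

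**The size rests on assumptions.** The protocol gives no non-response by arm, and it does not document that readmitted patients answer less often. The multiplier is also stronger than it sounds: at 10% loss it means 30% in those lost against 13.3% in responders, or 45% against 11.7%. In the extreme case (15% non-response, m = 3) it means 45% against 9.7%. This stands too, so the figures are illustrations.

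**Section 3.2 already opens the hospital file.** It does, but for the cause of a HUG stay, not for whether one occurred, and the sentence does not cover emergency visits. If a full search was intended, Section 4.3 and Table 2 do not say so.

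**Sections 4.2 and 5 promise to include everyone.** That is a fair reading of the intent. No source is named from which the missing readmission data would come, so the promise cannot be kept as written.

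**Stronger readings to avoid.** A reader might infer that the scheme flatters the intervention. The documents do not support that: if the D3 to D7 call improves response in the intervention arm, more of that arm's events are captured and the bias runs against the intervention. A reader might also set the 3.7 points beside the 3.75-point difference in Section 2, but that figure only shows why a readmission trial is infeasible and is not a target here. Nor does the plan state that non-responders are excluded; this follows from Sections 4.4 and 5.2 and conflicts with Sections 4.2 and 5.

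**Conclusion.** The point holds as a modest weakness in a secondary outcome. Occurrence of a readmission or emergency visit has one source, the patient at the call. Patients who die or cannot be reached are withdrawn, and neither a second source nor a missing-data rule covers them. The comparison would in practice be among responders.

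At the planned 10% loss and the assumed 2 to 3 times risk, a 15% rate would appear as 11.7% to 13.3%. A false difference arises only if response differs by arm. Under the assumed 5% v 15% split it is 0.9 to 6.2 points across rates of 7% to 25%, and its direction is not known in advance. The primary knowledge analysis is unaffected. The reason to act is that a better source is already open to the study staff: they consult the file for causes of readmission and for deaths, and participants are told that their records will be consulted (Section 4.2).

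**What to change.** - **Source.** In Section 3.2, in the readmission paragraph of Section 4.3 and in Table 2 items 91 and 92, establish readmissions and emergency visits within 30 days of discharge from the HUG computerised record. Do this for every randomised patient who has not withdrawn consent to record use, including those who died or did not answer.
- **Care outside HUG.** Add reports from the patient, relatives or the attending physician, the kinds of source already planned for death.
- **Section 4.4.** Amend it so that death or being unreachable by telephone does not end record-based follow-up. Without this edit the new source would contradict the rule that data are kept only up to the loss.
- **Analysis.** In Section 5, use these patients as the denominator, report by arm how many were ascertained from the record alone, and say how a death without readmission is counted.

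The cost is a few minutes of record look-up per patient by staff who already use the file. The repair is not complete: ambulatory visits and care at other hospitals may still be missed for non-responders. Responders would have two sources and some non-responders only one, which is why the count of record-only patients should be shown by arm.
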